## Additional Simulations Targeted to the Setting of the GRADUATE Trials

### Methods

We conducted a simulation study to further investigate the type I error control of the reference-based conditional mean imputation combined with the jackknife for inference. The set-up of the simulation study is similar to the simulations reported in [Wolbers et al. \(2022\)](#), but the simulation parameters and the scenarios considered are adapted to the GRADUATE trials. All simulations were for 1:1 randomized placebo-controlled trials with 508 subjects per group and visits at baseline and at 24, 52, 76, 104, and 116 weeks of follow-up. All simulations were performed under the null hypothesis of no difference in mean outcome trajectories between the groups. Scenarios including different probabilities of ICEs in the two groups and/or misclassification of SDCR ICEs as NSDCR ICEs were also included as described below.

Specifically, the other simulation parameters were chosen as follows:

- The mean outcome trajectory in both groups increased linearly from 3.65 to 4.65 during the first 52 weeks from baseline (i.e., an increase of 1 point in the first year), and increased linearly by 1.5 points per year afterwards.
- The variances of the outcomes at baseline and follow-up visits in both groups were: 1.53, 2.08, 2.65, 3.19, 4.26, 4.26.
- The correlation matrix of the baseline and follow-up values in both groups is shown on [Table 1](#).

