## **3. SAMPLE SIZE DETERMINATION**

Determination of sample size is based on participants enrolled in the global enrollment phase. In each study, approximately 1016 participants will be enrolled and randomized in 1:1 ratio to each treatment arm (active drug or placebo) during the global enrollment phase. The original planned sample size was of 760 participants, but it was increased to 1016 participants based on considerations from external studies (in protocol version 3).

Additional participants may be randomized during the China extension if at least 1 participant is enrolled at sites in mainland China, Hong Kong, or Taiwan that are recognized by the NMPA during the global enrollment phase.

The estimated sample size required to demonstrate efficacy with regard to Clinical Dementia Rating-Sum of Boxes (CDR-SB) is based on the following assumptions:

- the mean change in the CDR-SB from baseline to Week 104 is 2.5 points in the placebo arm
- a common standard deviation across treatment arms for change of approximately 2.97 from baseline to Week 104 in the CDR-SB
- active drug has a true effect of a 30% relative reduction in deterioration of CDR-SB

Based on these assumptions, and using a student's T-test with equal variance, a sample size was calculated for 90% power to detect a true treatment effect of 30% relative reduction in deterioration of CDR-SB at a two-sided  $\alpha$  of 0.05.

Uncertainties on parameters affecting the power (e.g., dropout rate, study drug discontinuation rate, standard deviation, and placebo decline) were assumed to be equivalent to a drop in sample size of up to around 35% and were corrected for accordingly. This calculation leads to a total of 1016 participants in the study.

At the date of writing Protocol Version 4, it was expected that participants would miss an average of 8 weeks of study drug administration over the course of the original two-year study due to the COVID-19 pandemic. This had the potential to decrease the power of the study from ~90% to ~80%. To mitigate the impact of missed administrations, the double-blind treatment period has been extended by 12 weeks. Under current assumptions, this brings the study power back to the originally planned ~90%.

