## Results

The overall probability for a subject to experience either a SDCR or a NSDCR event during the trial under the four scenarios is reported in [Table 3](#). These probabilities were estimated via simulation of a large trial with a sample size of 100'000 subjects per group.

**Table 3 Overall Probability for a Subject to Experience Either a SDCR or a NSDCR Event during the Trial under all the Scenarios Considered. Probabilities were Estimated via Simulation of a Large Trial with a Sample Size of 100'000 Subjects Per Group.**

	Scenario 1	Scenario 2	Scenario 3	Scenario 4
Probability of SDCR ICE (PLACEBO)	21%	17%	30%	27%
Probability of SDCR ICE (ACTIVE)	21%	24%	30%	33%
Probability of NSDCR ICE (PLACEBO)	11%	9%	0%	0%
Probability of NSDCR ICE (ACTIVE)	11%	12%	0%	0%
Overall ICE probability (PLACEBO)	32%	26%	30%	27%
Overall ICE probability (ACTIVE)	32%	36%	30%	33%

For each scenario considered, we assumed that a given fraction of SDCR ICEs had been misclassified as NSDCR ICEs. That is, we will apply a hypothetical strategy not only to those ICEs that are truly NSDCR, but also to a given fraction of SDCR events. The misclassification rate varied as follows: 0%, 15%, 30%, 45%, where 0% means that there is no misclassification of any SDCR event, while 45% means that 45% of SDCR events will be classified (and handled) as NSDCR events.

Type I error was simulated based on 10'000 simulated trials for each scenario. The respective misclassification rates were then applied to these data before the analysis. The analysis was consistent with the primary analysis of the GRADUATE trial, i.e., conditional mean imputation with jackknife-based inference (as described in [Wolbers et al. \[2022\]](#)) with copy-increments-in-reference (CIR) imputation for missing data after SDCR ICEs.

The simulation results are summarized in [Table 4](#). Simulated type I errors ranged from 4.69% to 5.18% across scenarios and misclassification rates. Simulations based on 10,000 simulated data sets provide a Monte Carlo standard error for type I error estimates of approximately  $\pm 0.22\%$ . Therefore, these results are fully consistent with strict type I error control at the 5% significance level.

**Table 4 Type I Error Rate Estimates for Each of the Scenarios and Misclassification Rates. Simulations are based on 10,000 Simulated Data Sets which Provide a Monte Carlo Standard Error for Type I Error Estimates of Approximately 0.22%.**

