### Conclusion

The primary analysis described in this SAP is based on the method described in [Wolbers et al. \(2022\)](#). This publication describes and justifies the method in detail and provides theoretical and simulation support that it controls type I error.

Clarification and details on the theoretical argument were provided and additional simulations were conducted. These simulations explored plausible scenarios calibrated to the GRADUATE studies. They also assessed the impact of ICE misclassification.

Based on this body of evidence, the proposed method for primary analysis (using conditional mean imputation of missing data combined with the jackknife for inference) adequately controls type I error.

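### Do the variances listed in SAP Appendix 1 undercut the stated ~90% power or the type I error evidence?

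*SAP*

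**What the plan says.** Appendix 1 of the SAP simulates trials with 508 participants per arm to check that conditional mean imputation with jackknife inference holds its 5% level. On the mean, "The mean outcome trajectory in both groups increased linearly from 3.65 to 4.65 during the first 52 weeks from baseline" and then "increased linearly by 1.5 points per year afterwards". On the spread, "The variances of the outcomes at baseline and follow-up visits in both groups were: 1.53, 2.08, 2.65, 3.19, 4.26, 4.26". Table 1 of the appendix puts the correlation of baseline with Weeks 104 and 116 at 0.52. Table 2 gives the visit-wise intercurrent-event probabilities, with SDCR odds rising 45% per outcome point. Table 3 reports the resulting overall event rates from a run of 100,000 per group, and Table 4 the type I error, including runs in which up to 45% of SDCR events are labelled NSDCR. The Methods state: "All simulations were performed under the null hypothesis of no difference in mean outcome trajectories between the groups". The Conclusion adds: "These simulations explored plausible scenarios calibrated to the GRADUATE studies".

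Section 3 of the SAP, like protocol Section 6.1, takes a placebo decline of 2.5 points at Week 104, a 30% relative effect, and "a common standard deviation across treatment arms for change of approximately 2.97 from baseline to Week 104 in the CDR-SB". It then allows for the equivalent of a sample-size drop of about 35%, naming four sources: dropout, study drug discontinuation, standard deviation and placebo decline. After the 12-week extension it says: "Under current assumptions, this brings the study power back to the originally planned ~90" per cent.

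**The concern.** The simulated decline at Week 104 is 1.0 + 1.5 = 2.5 points, exactly the planning value, so the setting seems meant to match the trial. The spread does not match: neither reading of the six numbers gives an SD of change of 2.97, and the reading as printed fails to return the appendix's own event table. If the simulation reflects what the sponsor believes about variability, the power statement might be too optimistic. If it does not, the description of the scenarios as calibrated looks too strong.

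A second worry concerns the misclassification rows. With identical mean trajectories in both arms, imputing from placebo increments and imputing from the participant's own arm agree in expectation. Relabelling an event might then seem unable to matter, which would make those rows uninformative.

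**Working it through.** **1. The plan's own sample size.** Effect 0.30 × 2.5 = 0.75; SD 2.97; two-sided 0.05; 90% power. n per arm = 2 × (1.960 + 1.282)² × 2.97² / 0.75² ≈ 330, so 660 in total, and 660 / 0.65 ≈ 1016. t-test power at 330 per arm is 90.0%. Section 3 reproduces.

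**2. Table 3 under each reading.** I simulated the stated means, correlations and logistic event model with 2,000,000 participants per cell. Events were possible after the visits from baseline to Week 104, and SDCR took precedence at a tie.

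| SDCR probability, % | Table 3 | As variances | As SDs |
|---|---|---|---|
| Scenario 1, both arms | 21 | 16.2 | 21.1 |
| Scenario 2, placebo | 17 | 12.8 | 17.3 |
| Scenario 2, active | 24 | 19.5 | 24.5 |
| Scenario 3, both arms | 30 | 24.4 | 29.9 |
| Scenario 4, placebo | 27 | 21.0 | 26.5 |
| Scenario 4, active | 33 | 27.6 | 33.1 |

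On the SD reading the NSDCR rates are 10.6% (Scenario 1) and 8.8% and 12.3% (Scenario 2), printed as 11, 9 and 12. The Monte Carlo standard error of a Table 3 entry is at most about 0.15 points, so gaps of 4 to 6 points under the variance reading are not noise. Other visit conventions do not rescue that reading. Weeks 24 to 116 leave gaps of up to 1.7 points. Baseline to Week 116 gives NSDCR 12.6% against 11% and Scenario 4 active SDCR 35.2% against 33%.

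**3. Implied SD of change to Week 104**, √(s₀² + s₁² − 2 × 0.52 × s₀ × s₁):

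- as variances: √(1.53 + 4.26 − 2 × 0.52 × 1.237 × 2.064) = √3.135 = 1.77
- as SDs: √(2.341 + 18.148 − 2 × 0.52 × 1.53 × 4.26) = √13.71 = 3.70

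**4. Power at SD 3.70.** (3.70 / 2.97)² ≈ 1.554, equivalent to a sample-size drop of 1 − 1/1.554 ≈ 36%. That is the size of the allowance in Section 3, which lists the SD among its causes.

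| Effect | 508 per arm | 406 (a further 20% lost, my assumption) | 330 (a further 35% lost) |
|---|---|---|---|
| 0.75 (30% of 2.5, Week 104) | 89.7% | 82% | 73.8% |
| 0.854 (30% of the simulated Week 116 decline) | 95.7% | – | 84.1% |

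The Week 116 decline is 1 + 1.5 × 64/52 = 2.846, and 0.30 × 2.846 = 0.854.

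**5. Type I error and scale.** Hold the correlations and the pattern of events and missing data fixed, and multiply every deviation from the mean by a common factor, such as 2.97 / 3.70 = 0.80. Under the null the treatment estimate and its jackknife standard error both change by that factor, so the Z-score does not move. Spread then acts only through the event rates. Overall event rates in Table 3 run from 26% to 36%, and Table 4 stays between 4.69% and 5.18%, with a Monte Carlo standard error of about 0.22 points.

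**6. The misclassification rows.** The two imputation rules agree at the true means, but each trial uses estimated means. A relabelled event also discards the later data of the 20% who stay in the study. In a simplified null version of Scenario 4 (1,500 trials, SD reading, no intermittent missing data), 45% misclassification left the estimate centred (−0.007 against −0.008) but raised its SD from 0.217 to 0.237. The variance ratio is (0.237 / 0.217)² ≈ 1.19. Whether the jackknife tracks such a change is a genuine type I error question, and Table 4 addresses it.

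**The case for a change.** The best case for a change runs as follows. If the SD really were 3.70, it alone would use up the 35% allowance and leave nothing for the other three causes that the allowance names. Appendix 1 itself assumes such losses. In Scenario 1, 21% × 80% + 11% ≈ 28% of participants have no later data, leaving about 367 of 508 per arm, and crude power for 0.75 points is then about 78%. The appendix is also the SAP's trial-specific evidence for its primary method, so it ought to reproduce as printed.

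The last point stands: the label is wrong as printed, and nothing reconciles the spread with 2.97. The power argument is weaker. The 78% ignores what the longitudinal imputation model recovers from earlier visits, and it sets the Week 104 effect against a Week 116 analysis; with 0.854 points the same 367 per arm give about 88%. Nor does the appendix offer its covariance as a revised planning SD. It was set up to test type I error, and a normal model with SD 4.26 around a Week 116 mean of 6.50 puts about 6% of scores below zero on a 0 to 18 scale.

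Misclassification under a real effect would shift the estimate: with a 30% effect and 45% misclassification the mean difference moves by 4% to 8%, for example from −0.76 to −0.81. That is a question of bias rather than of type I error. The SAP already covers robustness here through the treatment policy estimand in Section 5.3.5.2, which treats all events alike, and the tipping point analysis in Section 5.3.4.

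**Conclusion.** No change to the plan is called for. The six values in Appendix 1 are standard deviations printed as variances, on the evidence of Table 3. The implied SD of change of 3.70 differs from the planning 2.97 without explanation. Both are matters of reporting in a supporting appendix. They alter no analysis, sample size or decision rule, and correcting the word would change no result.

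The stated power of about 90% is not shown to be wrong. For 0.75 points at SD 3.70 it is 89.7% when the SD is the only departure from plan. It reaches 74% only if a further full 35% of participants is lost to other causes, and for 0.854 points the range is 84% to 96%. The type I error conclusion does not hinge on the scale, and the misclassification rows test what a null simulation should test.

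This rests on two assumptions: that events could follow the visits from baseline to Week 104, the convention that best fits Table 3, and that Table 4 came from the same code and inputs as Table 3. Table 4 itself was not rerun.

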**Table 1 Correlation Matrix**

	Baseline	Week 24	Week 52	Week 76	Week 104	Week 116
Baseline	1	0.72	0.60	0.54	0.52	0.52
Week 24	0.72	1	0.72	0.60	0.54	0.54
Week 52	0.60	0.72	1	0.72	0.60	0.60
Week 76	0.54	0.60	0.72	1	0.72	0.72
Week 104	0.52	0.54	0.60	0.72	1	0.85
Week 116	0.52	0.54	0.60	0.72	0.85	1

- Two types of intercurrent events were simulated: Study Drug or Condition Related ICEs (SDCR) and Non-Study Drug or Condition Related ICEs (NSDCR).
- Simulation of SDCR ICEs:
  - The probability of an SDCR ICE after each visit was calculated according to a logistic model, which also depended on the observed outcome at that visit.
  - The visit-wise probability of an SDCR ICE for a subject with an observed outcome at that visit of 3.65 was varied across 4 different scenarios as reported in [Table 2](#).
  - The odds of an SDCR ICE further increased by 45% for each 1 point increase in the observed outcome.
  - In the placebo group, an SDCR ICE had no effect on the mean trajectory. In the active group, subjects who experienced an SDCR ICE followed the slope of the mean trajectory from the placebo group from that time point onward (CIR).
  - Study drop-out after the SDCR ICE visit occurred with a probability of 80% leading to missing outcome data from that time point onward.
- Simulation of NSDCR ICEs:
  - The probability of an NSDCR ICEs after each visit was assumed to be independent of the visit and the observed outcome. The specification of these probabilities for each of the 4 scenarios is presented in [Table 2](#).
  - NSDCR ICEs always led to missing outcome data from that time point onward.
- If both SDCR and NSDCR ICEs were simulated to occur for a subject, then it was assumed that only the earlier of them counted. In case both ICEs were simulated to occur at the same time, the event was considered a SDCR ICE. This means that a single subject could experience either a SDCR or a NSDCR ICE, but not both of them.
- Additional missing data unassociated with an ICE was simulated by assuming that a subject missed any visit with a probability of 5%.

**Table 2 Specifications of ICEs Probabilities in Each Group for the Four Simulation Scenarios. Only the Parameters that Varied Across Different Scenarios are Presented in this Table.**

	Scenario 1	Scenario 2	Scenario 3	Scenario 4
Probability of a SDCR ICE after each visit for a subject with outcome equal to 3.65 (PLACEBO)	2%	1.5%	3%	2.5%
Probability of a SDCR ICE after each visit for a subject with outcome equal to 3.65 (ACTIVE)	2%	2.5%	3%	3.5%
Probability of a NSDCR ICE after each visit (PLACEBO)	2.5%	2%	0%	0%
Probability of a NSDCR ICE after each visit (ACTIVE)	2.5%	3%	0%	0%

Scenario 1 specifies equal ICE probabilities for the two groups, while Scenario 2 specifies a higher probability of both SDCR and NSDCR events in the active group compared to the placebo group. Scenario 3 simulates only SDCR events, with equal probabilities across the two groups. Scenario 4 also simulates only SDCR events, but with a higher probability in the active group.

## Results

The overall probability for a subject to experience either a SDCR or a NSDCR event during the trial under the four scenarios is reported in [Table 3](#). These probabilities were estimated via simulation of a large trial with a sample size of 100'000 subjects per group.

**Table 3 Overall Probability for a Subject to Experience Either a SDCR or a NSDCR Event during the Trial under all the Scenarios Considered. Probabilities were Estimated via Simulation of a Large Trial with a Sample Size of 100'000 Subjects Per Group.**

	Scenario 1	Scenario 2	Scenario 3	Scenario 4
Probability of SDCR ICE (PLACEBO)	21%	17%	30%	27%
Probability of SDCR ICE (ACTIVE)	21%	24%	30%	33%
Probability of NSDCR ICE (PLACEBO)	11%	9%	0%	0%
Probability of NSDCR ICE (ACTIVE)	11%	12%	0%	0%
Overall ICE probability (PLACEBO)	32%	26%	30%	27%
Overall ICE probability (ACTIVE)	32%	36%	30%	33%

For each scenario considered, we assumed that a given fraction of SDCR ICEs had been misclassified as NSDCR ICEs. That is, we will apply a hypothetical strategy not only to those ICEs that are truly NSDCR, but also to a given fraction of SDCR events. The misclassification rate varied as follows: 0%, 15%, 30%, 45%, where 0% means that there is no misclassification of any SDCR event, while 45% means that 45% of SDCR events will be classified (and handled) as NSDCR events.

Type I error was simulated based on 10'000 simulated trials for each scenario. The respective misclassification rates were then applied to these data before the analysis. The analysis was consistent with the primary analysis of the GRADUATE trial, i.e., conditional mean imputation with jackknife-based inference (as described in [Wolbers et al. \[2022\]](#)) with copy-increments-in-reference (CIR) imputation for missing data after SDCR ICEs.

The simulation results are summarized in [Table 4](#). Simulated type I errors ranged from 4.69% to 5.18% across scenarios and misclassification rates. Simulations based on 10,000 simulated data sets provide a Monte Carlo standard error for type I error estimates of approximately  $\pm 0.22\%$ . Therefore, these results are fully consistent with strict type I error control at the 5% significance level.

**Table 4 Type I Error Rate Estimates for Each of the Scenarios and Misclassification Rates. Simulations are based on 10,000 Simulated Data Sets which Provide a Monte Carlo Standard Error for Type I Error Estimates of Approximately 0.22%.**

Scenario	ICE misclassification rate (from SDCR to NSDCR)	Type I error
Scenario 1	0%	4.95%
	15%	4.84%
	30%	4.97%
	45%	4.83%
Scenario 2	0%	5.11%
	15%	5.00%
	30%	5.18%
	45%	5.13%
Scenario 3	0%	4.98%
	15%	4.81%
	30%	4.82%
	45%	4.69%
Scenario 4	0%	4.73%
	15%	4.78%
	30%	5.00%
	45%	5.01%

### Conclusion

The primary analysis described in this SAP is based on the method described in [Wolbers et al. \(2022\)](#). This publication describes and justifies the method in detail and provides theoretical and simulation support that it controls type I error.

Clarification and details on the theoretical argument were provided and additional simulations were conducted. These simulations explored plausible scenarios calibrated to the GRADUATE studies. They also assessed the impact of ICE misclassification.

Based on this body of evidence, the proposed method for primary analysis (using conditional mean imputation of missing data combined with the jackknife for inference) adequately controls type I error.

## Appendix 2 ADCS-ADL Dependence Scale Algorithm Version 2.1

### Item Domains Used in the Algorithm

- bADL - basic Activities of Daily Living: Questions 1-5, 6B
- iADL – instrumental Activities of Daily Living
  - Household Activities: Questions 6A, 7, 10-14, 23
  - Communication and Engagement: Questions 17, 21, 22
  - Outside Activities: Questions 15, 16A, 16B, 18

Note that 4 items included in the original communication and engagement algorithm are not included in the updated algorithm. Specifically concentrating on a television programme (Q8), participating in small talk (Q9), talking about current events (Q19), recalling information recently read in book/magazine (Q20) were excluded. Whilst these concepts are clearly important to quality of life, they do not require supervision and are therefore not considered fundamental to independence.

The algorithm starts by checking the requirements for Level 5 which is the highest level of impairment and continues to check each lower level until the patient meets the requirements of a level and is assigned to that level. If a patient does not meet the requirements for any of Levels 1-5, then the patient is assigned Level 0.

- **Level 0:** is the dependence level assigned when a patient has no recorded impairment
- **Level 1:** Item score = 2 on one or more items from only one of the following clusters: Household Activities, Communication and Engagement, Outside Activities. There should be no bADL impairment.
- **Level 2:** Item Score = 2 on one or more items from two or more of the following clusters: Household Activities, Communication and Engagement, Outside Activities, OR Item Score  $\leq 1$  on one or more items from any of the following clusters: Household Activities, Communication and Engagement. (There should be no bADL impairment).
- **Level 3:** Item Score  $\leq 2$  for all items from the following clusters: Household Activities, Communication and Engagement, Outside Activities, OR Item Score  $\leq 1$  on one or more items from Outside Activities, OR Item Score = 2 for Bathing (Q4), Score = 2 for toileting (Q3), Score = 3 for dressing, score = 1 or 2 for eating OR Item score = 2 for walking
- **Level 4:** Any one of the following: Item Score  $\leq 2$  for Grooming (Q5), Item score  $\leq 1$  for Bathing (Q4) item score = 1 for toileting (Q3) or Item score  $\leq 2$  for dressing, OR item score = 0 for Eating (Q1) or Item score = 1 for walking
- **Level 5:** Item Score = 0 for either Walking (Q2) or Toileting (Q3)

